18.4. Descriptive Statistics

In general, descriptive statistics for continuous variables will include number of nonmissing values, arithmetic mean, standard deviation, median, minimum, and maximum. Descriptive statistics for PK parameters will include number of observations, arithmetic mean, standard deviation, arithmetic coefficient of variation (%CV), median, minimum, maximum, geometric mean and geometric %CV. Categorical variables will be summarized using percentages and frequency counts, by cohort and time point.

18.5. Demographics, Baseline Characteristics, and Subject Disposition

All subjects will be included in the summary of subject disposition, which will summarize the frequency and percentage of subjects screened and treated who completed or discontinued from the study, along with reason for discontinuation, by cohort. Demographics and baseline characteristics will be summarized for all subjects by each cohort and overall.

18.6. Safety Analysis

Safety analyses will be performed on the safety population, and will be reported by each cohort. Safety analyses will include an analysis of all AEs, ECGs, clinical laboratory data, physical examinations, and vital sign measurements, and will be presented using descriptive statistics. No inferential statistical analyses are planned on the safety parameters of this study. The incidence of treatment-emergent AEs and SAEs will be summarized, by system organ class and preferred term for each cohort and overall, by relationship to study drug. Treatment-emergent AEs will also be summarized by cohort and overall by severity. Serious AEs and AEs resulting in withdrawal from the study will be listed. Subjects having multiple AEs within a category (eg, overall, system organ class, preferred term) will be counted once in that category. For severity tables, a subject's most severe event within a category will be counted.

Changes from baseline in vital sign measurements and laboratory assessments (eg, chemistry, CBC with differential, and urinalysis) will be summarized by each cohort. Laboratory parameter values will be graded according to the CTCAE. Shift tables by cohort will be produced for these laboratory parameters. These tables will summarize the number of subjects with each baseline grade relative to the reference ranges and changes to the worst highest grade assessed post-dose during the study.

The ECG parameters will be measured at the specified time points, including heart rate, PR, RR, QRS, QT, and corrected QTcF intervals. The average of the triplicate ECG readings at the time points collected will be calculated, and changes from pretreatment baseline values will be assessed by each cohort.

An outlier analysis will be performed that will summarize the frequency and percentage of subjects who meet any of the following outlier criteria at each visit by cohort:

- QT, QTcF interval > 450 msec
- QT, QTcF interval > 480 msec
- QT, QTcF interval > 500 msec
- QT, QTcF interval increases from baseline > 30 msec
- QT, QTcF interval increases from baseline > 60 msec

All concomitant medications will be coded using the WHO Drug Dictionary, and the frequency and percentage of concomitant medications will be summarized.

18.7. Pharmacokinetic Analysis

The individual serum concentration data for ALXN1210-treated subjects, with actual sampling dates and times, will be used to derive the PK parameters by noncompartmental analyses methods using Phoenix WinNonlin 6.3 or higher.

The following PK parameters will be derived: maximum observed serum concentration (C_{max}), time to maximum observed serum concentration (T_{max}), area under the serum concentration versus time curve from time zero to the last quantifiable concentration (AUC_t) area under the curve from time zero to infinity (AUC_{∞}), terminal elimination rate constant (λ_z), terminal elimination half-life ($T_{\frac{1}{2}}$), total clearance (CL or CL/F), and volume of distribution (V_d or V_d/F).

The geometric means ratio (ALXN1210 SC/ALXN1210 IV) and its 90% CI will be computed for C_{max} , AUC_t, and AUC_{∞}, and will be tabulated. The CI will be computed using the between-subject variance. Assessments of concentration over time will be presented.

Further details will be provided in the Statistical Analysis Plan (SAP).

18.8. Pharmacodynamic and Immunogenicity Analyses

The PD effects of ALXN1210 SC and IV will be evaluated by assessing changes in serum total and free C5 concentrations, cRBC hemolysis, and other measures of C5 activation over time. Analyses will be performed on samples collected as described in the Schedule of Assessments (Section 9).

Immunogenicity, as measured by ADA, will be summarized in tabular form by cohort and by-subject listings.

18.9. Interim Analysis

An interim analysis may be performed as needed.

19. DIRECT ACCESS TO SOURCE DATA/DOCUMENTS

19.1. Study Monitoring

Before a study center can enter a subject into the study, a representative of Alexion (sponsor) will visit the investigational study center to do the following:

- Determine the adequacy of the facilities;
- Discuss with the investigator(s) and other personnel their responsibilities with regard to protocol adherence, and the responsibilities of the sponsor or designee.

During the study, a monitor from the sponsor and/or designee will have regular contact with the study center, to do the following:

- Provide information and support to the investigator;
- Confirm that facilities remain acceptable;
- Confirm that the investigational team is adhering to the protocol, that data are being accurately recorded on the eCRF, and that investigational product accountability checks are being performed;
- Perform source data verification. This includes a comparison of the data on the eCRF with the subject's medical records at the hospital or practice, and other records relevant to the study. This will require direct access to all original records for each subject (eg, clinic charts);
- Record and report any protocol deviations not previously sent to the sponsor or designee; and
- Confirm that AEs and SAEs have been properly documented on the eCRF, and confirm that any SAEs have been forwarded to the sponsor or designee, and those SAEs that met criteria for reporting have been forwarded to the IRB/IEC.

The monitor will be available between visits if the investigator(s) or other staff needs information or advice.

19.2. Audits and Inspections

Authorized representatives of the sponsor or designee, a regulatory authority, or an IRB/IEC may visit the study center to perform audits or inspections, including source data verification. The purpose of an audit or inspection is to systematically and independently examine all study-related activities and documents to determine whether these activities were conducted, and data were recorded, analyzed, and accurately reported, according to the protocol, Good Clinical Practice (GCP) guidelines of the International Council for Harmonisation (ICH), and any applicable regulatory requirements. The investigator is expected to contact the sponsor immediately if contacted by a regulatory agency about an inspection.

19.3. Institutional Review Board/Independent Ethics Committee

The investigator must obtain IRB/IEC approval for the clinical study (see Section 21.1). Initial, subsequent, and ongoing IRB/IEC approvals, and all materials approved by the IRB/IEC for this study, including the subject consent form and recruitment materials, must be maintained by the investigator and made available for inspection.

19.4. Safety Review Committee

Since its primary function will be to ensure subject safety, the members of the SRC will have access to all clinical and safety data. For additional details regarding the SRC, please see Section 8.5.

19.5. Regulatory Agency

As required by the Medicines and Healthcare products Regulatory Agency (MHRA), a Clinical Trial Application will be submitted before the beginning of the study and a Notice of Acceptance Letter must be received prior to screening.

20. QUALITY CONTROL AND QUALITY ASSURANCE

To ensure compliance with GCP and all applicable regulatory requirements, the sponsor or designee may conduct a quality assurance audit. Please see Section 19.2 for more details regarding the audit process.

21. ETHICS

21.1. Ethics Review

The final study protocol and the final version of the ICF must be approved or given a favorable opinion in writing by an IRB/IEC, as appropriate. The investigator must submit written approval to the sponsor or designee prior to screening subjects.

The investigator is responsible for informing the IRB/IEC of any amendment to the protocol, in accordance with local regulatory requirements. The IRB/IEC must review and approve all protocol amendments prior to implementation at the study center. The IRB/IEC will review the protocol at least annually or as local regulations require. In addition, the IRB/IEC must approve all advertising used to recruit subjects for the study.

The investigator is also responsible for informing the IRB/IEC of any reportable serious adverse drug reactions from any other study conducted with the investigational product. The sponsor or designee will provide this information to the investigator.

Progress reports and notifications of serious adverse drug reactions will be provided to the IRB/IEC, according to local regulations and guidelines.

21.2. Ethical Conduct of the Study

The study will be performed in accordance with ethical principles that have their origin in the Declaration of Helsinki and are consistent with ICH, GCP, applicable regulatory requirements, and Alexion's policy on bioethics.

21.3. Written Informed Consent

The investigator will ensure that the subject is given full and adequate oral and written information about the nature, purpose, possible risk, and benefit of the study. Subjects must also be notified that they are free to discontinue from the study at any time. The subject should be given the opportunity to ask questions and allowed time to consider the information provided.

The subject's signed and dated ICF must be obtained before conducting any study procedures, and documented in the subject's study record.

The investigator must maintain the original of all signed ICF versions. A copy of the signed ICF(s) must be given to the subject.

21.4. Urgent Safety Measures

If an event occurs that is related to the conduct of the study or the development of the study drug, and this new event is likely to affect the safety of subjects, the sponsor and the investigator will take appropriate urgent safety measures to protect subjects against any immediate hazard. The sponsor will work with the investigator to ensure the IRB/IEC is notified. The sponsor will also inform the Medicines and Healthcare Products Regulatory Agency (MHRA).

22. DATA HANDLING AND RECORDKEEPING

22.1. Inspection of Records

The sponsor or designee will be allowed to conduct study center visits to the investigation facilities for the purpose of monitoring any aspect of the study. The investigator agrees to allow the monitor to inspect the drug storage area, study drug stocks, drug accountability records, subject charts, and study source documents, and other records relative to study conduct. See also Section 20 regarding audits.

22.2. Retention of Records

The study center will maintain adequate study records according to local regulatory requirements after completion or termination of the study or for a minimum period of 5 years. After that period, the sponsor will be contacted to determine whether the study records will be forwarded to the sponsor, destroyed, or kept at the study center or another facility for a longer period of time, at the sponsor's expense. If it becomes necessary for the sponsor or designee or the regulatory authority to review documentation relating to the study, the investigator must permit access to such records.

23. PUBLICATION POLICY

The terms for publication are outlined in the Clinical Study Agreement, Statement of Agreement, or the Master Clinical Study Agreement. Refer to these documents for further details and information.

25. APPENDICES

Appendix 1 Acute Infusion Reactions

Appendix 2 United Kingdom Resuscitation Council Anaphylaxis Algorithm

APPENDIX 1. ACUTE INFUSION REACTIONS ALGORITHM

* National Cancer Institute Common Terminology Criteria (NCI CTC) for AEs (NCI CTCAE, version 4.0)

APPENDIX 2. UNITED KINGDOM RESUSCITATION COUNCIL ANAPHYLAXIS ALGORITHM

1. INTRODUCTION

The purpose of this Statistical Analysis Plan (SAP) is to define the variables and analysis methodology to address the study objectives.

The protocol dated 28 Jul 2016, Amendment 2, was used in the preparation of this SAP.

Pharmacokinetic parameters will be calculated by Alexion or its designee. Richmond Pharmacology Ltd (RPL) is responsible for performing statistical analyses. Tables, figures, and listings will be produced using Statistical Analysis Software (SAS), Version 9.3 or higher.

2. STUDY OBJECTIVES AND ENDPOINTS

2.1 Study objectives

The objectives of this study are:

Primary

- To evaluate the safety and tolerability of a single dose of ALXN1210 subcutaneous (SC) compared to ALXN1210 intravenous (IV) in healthy subjects, as assessed by physical examination findings, vital sign measurements, immunogenicity, laboratory analysis, and assessments of adverse events (AEs).
- To determine the absolute bioavailability of ALXN1210 SC.

Secondary

• To evaluate the pharmacodynamic (PD) effects of ALXN1210 SC compared to ALXN1210 IV, as assessed by the level of free C5 and chicken red blood cell (cRBC) hemolysis.

2.2 ENDPOINTS

The safety, immunogenicity, pharmacokinetics (PK), and PD endpoints are described in the sections to follow. The timing of assessments is displayed in the Schedule of Assessments (see protocol).

Safety Endpoints

Safety endpoints include the following:

- Change from baseline in physical examination findings
- Change from baseline in vital sign measurements
- Incidence of antidrug antibodies (ADA) measured via immunogenicity testing
- Change from baseline in electrocardiogram (ECG) parameters
- Change from baseline in laboratory measurements
- Incidence of AEs and serious AEs (SAEs)

Pharmacokinetic Endpoints

The following PK parameters will be evaluated:

- Maximum observed serum concentration (C_{max})
- Time to maximum observed serum concentration (t_{max})
- Area under the serum concentration versus time curve from time zero to the last quantifiable concentration $({\sf AUC}_t)$
- Area under the serum concentration versus time curve from time zero to infinity (AUC $_{\infty}$)
- Terminal elimination rate constant (λ_z)
- Terminal elimination half-life $(t_{1/2})$
- Total body clearance of drug from the serum (CL or CL/F)
- Apparent volume of distribution during terminal phase (V_d or V_d/F)

Pharmacodynamic Endpoints

The following PD effects will be evaluated:

- Change in serum total and free C5 concentrations over time
- Change in cRBC hemolysis over time

3. NUMBER OF SUBJECTS AND RANDOMIZATION

3.2 Number and Source of Subjects

Forty-two subjects are planned for evaluation of the primary and secondary objectives in this study: 6 (4 ALXN1210 SC, 2 placebo SC) subjects in Cohort 1a; 24 (20 ALXN1210 SC, 4 placebo SC) subjects in Cohort 1b, and 12 (ALXN1210 IV) subjects in Cohort 2. At the sponsor's discretion, up to 8 additional subjects (2 subjects each in Cohorts 1a and 1b and 4 subjects in Cohort 2) may be enrolled into the study if 2 or more subjects discontinue within 3 months for reasons other than drug-related AEs, and after consultation with the Safety Review Committee (SRC).

3.3 Randomization and Blinding

Eligible subjects who meet the inclusion and exclusion criteria will be assigned unique numbers for enrollment and randomization. The randomization list will be generated using SAS PROC PLAN by a statistician not involved in the development of this SAP and analyses.

This is a partially blinded study such that:

 Cohort 1a. Dosing (a single 400-mg dose of ALXN1210 SC or placebo SC) is double-blind. Subjects in Cohort 1a will be randomly assigned in a 2:1 ratio (4 ALXN1210 SC, 2 placebo SC; N = 6).

Subjects will be randomized in consecutive subject number order as per the above list. Randomization will occur at the point of study drug dosing.

Within Cohort 1a, the treatment will be allocated with permuted block randomization (blocksize = 3).

- Thirty-six subjects will be randomly assigned, in a 2:1 ratio, to either Cohort 1b (N=24) or Cohort 2 (N=12) (blocksize = 6).
 - Cohort 1b. Dosing (a single 400-mg dose of ALXN1210 SC or placebo SC) is double-blind. Subjects in Cohort 1b will be randomly assigned in a 5:1 ratio (20 ALXN1210 SC, 4 placebo SC; N = 24). Within Cohort 1b, the treatment will be allocated with permuted block randomization (blocksize = 12).
 - Cohort 2. Dosing (a single 400-mg dose of ALXN1210 IV) is openlabel (N = 12); both subjects and onsite medical/nursing staff will know the study drug/dose being administered.

Subjects will be randomized in consecutive subject number order as per the above list. Randomization will occur at the point of study drug dosing.

For the blinded part of the randomization schedule, (Cohort 1b) only pharmacy staff preparing the SC injections will be aware of treatment allocation. The finished doses will be labelled in a double blind fashion, thus protecting the study blind for all other staff and study subjects but the unblinded members of the pharmacy team.

Details of the subject enrollment and assignment of randomization can be found in the Study Operations Manual, Section 6.

4. STATISTICAL ANALYSES

In general, descriptive statistics for continuous variables will include number of observations, mean, standard deviation (SD), median, minimum, and maximum, by treatment group.

Descriptive statistics for PK parameters will include number of observations, arithmetic mean, SD, arithmetic coefficient of variation (CV), geometric mean, geometric CV, median, minimum and maximum, by treatment group.

Descriptive statistics for PD parameters will include number of observations, arithmetic mean, SD, median, minimum, and maximum, by treatment group.

Categorical variables will be summarized using frequency counts and percentages by treatment group.

The analyses will be presented by treatment group. Treatment group refers to ALXN1210 SC-, ALXN1210 IV-, and ALXN1210 SC placebo- treated subjects.

Baseline will be defined as the last value of the assessment recorded prior to first administration of study drug (ALXN1210 IV, ALXN1210 SC, or placebo SC). For post-dose assessments, the first scheduled value will be used for summary analysis if repeated measurements are made at a time point.

Deviations from the planned analyses will be described in the final integrated clinical study report (CSR).

4.1. Analysis Populations

The safety population will consist of all subjects who receive the protocol-defined, single dose of study drug (ALXN1210 IV, ALXN1210 SC, or placebo SC). Subjects in this population will be used for the safety analysis.

The PK population will consist of all subjects from the safety population who received either ALXN1210 SC or ALXN1210 IV and who have sufficient serum concentration data to enable the calculation of PK parameters. The PK population will be used for PK summaries.

The PD population will consist of all subjects from the safety population who have sufficient total and free C5 concentration data and cRBC hemolysis data. The PD population will be used for PD summaries.

The immunogenicity analysis population will consist of all subjects from the safety population who have a pre-dose and post-dose ADA sample collected.

Inclusion and exclusion from each analysis set will be decided at the Blind Data Review Meeting prior to database lock.

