In general, descriptive statistics for continuous variables will include number of nonmissing values, arithmetic mean, standard deviation, median, minimum, and maximum. Descriptive statistics for PK parameters will include number of observations, arithmetic mean, standard deviation, arithmetic coefficient of variation (%CV), median, minimum, maximum, geometric mean and geometric %CV. Categorical variables will be summarized using percentages and frequency counts, by cohort and time point.

Safety:

All subjects who received at least 1 dose of study drug will be included in the safety analysis. Safety data will be assessed using descriptive statistics. No inferential statistical analyses are planned on the safety parameters of this

study. Safety analysis will include an analysis of all AEs, laboratory values, ECGs, and vital sign measurements.

Shift tables will be produced for selected laboratory parameters. These tables will summarize the number of subjects with each baseline grade relative to the normal ranges and changes to the worst highest grade assessed post-dose during the study.

Pharmacokinetics/Pharmacodynamics:

Individual PK parameters (including descriptive statistics as follows: number of observations, arithmetic mean, standard deviation, arithmetic coefficient of variation [CV], median, minimum, maximum, geometric mean, and geometric CV) will be determined for the ALXN1210-treated subjects.

The PD effects of ALXN1210 SC and IV will be evaluated by assessing changes in serum total and free C5 concentrations, cRBC hemolysis, and other measures of C5 activation over time, using descriptive statistics.

Immunogenicity:

Immunogenicity, as measured by ADA, will be summarized in tabular form by cohort and by-subject listings.

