5.1.1. Clinical Studies

ALXN1210 has been administered safely to healthy subjects in 200 mg and 400 mg intravenous (IV) doses in a single ascending dose (SAD) study (Study ALXN1210-HV-101, N = 10). Healthy subjects have also been administered multiple 400 mg and 800 mg IV doses on an every 4 week (Q4W) regimen in an ongoing multiple ascending dose (MAD) study (Study ALXN1210-HV-102, N = 12). The starting doses of ALXN1210 IV in these 2 healthy volunteer studies were selected to assess safety in healthy volunteers and to have measurable pharmacologic activity (eg, inhibition of complement activation) based on the therapeutic exposure required with eculizumab. No safety concerns have been identified in either of the Phase 1 studies, both of which were randomized, blinded, and placebo controlled. In the completed Study ALXN1210-HV-101 (SAD), no serious adverse drug reactions, treatment discontinuations, or deaths were reported.

Conclusions from Study ALXN1210-HV-101 are as follows:

- ALXN1210 exhibited prolonged pharmacokinetic (PK) exposure with mean geometric half-life estimates of 32.4 days and 30.8 days following single doses of 200 and 400 mg, respectively.
- The PK parameters (area under the serum concentration versus time curve from time zero to the last quantifiable concentration $[AUC_t]$, area under the curve from time zero to infinity $[AUC_{\infty}]$, and maximum observed serum concentration $[C_{max}]$) increased in a slightly less than dose-proportional manner over the studied range of 200 to 400 mg based on the protocol-specified statistical analysis.

- Following single 200 mg and 400 mg doses of ALXN1210 IV, all 6
 pharmacodynamic (PD) variables (total complement C5 serum concentration, free
 complement C5 serum concentration, chicken red blood cell [cRBC] hemolysis,
 classical complement pathway [CCP] activity, complement alternative pathway
 [CAP] activity, and plasma C5b-9 activity) showed dose-dependent reductions from
 baseline. The effect of ALXN1210 on these PD variables was immediately evident
 after end of infusion (EOI). At the EOI, the mean free C5 serum concentrations and
 cRBC hemolysis activity were inhibited by > 99% and > 97%, respectively.
- The duration of the effect was longer following a 400-mg dose than a 200-mg dose.
- All subjects were negative for antidrug antibody (ADA) through Day 150.

In addition, multiple doses of ALXN1210 IV have been administered to patients with PNH.

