10.3. Subject Withdrawal Criteria

A subject may withdraw from the study at any time at his or her own request, or may be withdrawn at any time at the discretion of the investigator for safety, behavioral, or administrative reasons. Subjects who discontinue dosing will be instructed to return for follow-up visits as described in the Schedule of Assessments (Section 9).

Unless the investigator and sponsor agree to an alternative regimen, all subjects will take prophylactic antibiotics (oral penicillin V 500 mg twice daily) until complement activity has normalized (as determined by CH50 assay).

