12.5. Administration

12.5.1. Administration of ALXN1210 SC and Placebo SC

All doses of ALXN1210 SC or placebo SC will be administered by four 100-mg SC injections of 1 mL each (Table 7) in the abdominal area. All four 1-mL injections should be administered over a 15-minute period, and there should be at least 15 minutes between the end of injection in one subject and the start of injection in the next subject.

Cohort	Study drug and dose	Number of 1-mL syringes prepared	Total volume administered
1a	1 dose of 400 mg ALXN1210 SC or placebo SC	4	4 mL
1b	1 dose of 400 mg ALXN1210 SC or placebo SC	4	4 mL

Table 7: Dosing Reference Chart for ALXN1210 SC and Placebo SC Preparation

For further information regarding the preparation and administration of study drug, please see the pharmacy manual. Please refer to the SOM for additional information regarding blinding and study drug administration.

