12.6. Management of Potential Adverse Events During Study Drug Administration

Some subjects treated with IV infusions of mAbs have experienced concurrent infusion-related reactions with signs or symptoms that can be classified as acute allergic reactions/ hypersensitivity reactions or cytokine release syndrome.

Subjects will be closely monitored during and after study drug administration for any symptoms of anaphylaxis and other hypersensitivity reactions, including circulatory and/or respiratory changes or arrest, or urticaria, arthralgias, myalgias, or other signs of related reactions. Adequate treatment will be immediately available. Infusion-associated AEs may occur, and depending on their type and severity, discontinuation of infusion may be required. Subjects will be informed of early symptoms and signs of hypersensitivity reactions including hives, swollen face, eyelids, lips, or tongue, or trouble with breathing. An acute infusion-reaction algorithm will be used to manage infusion-related reactions (see Appendix 1: Acute Infusion Ste reactions Algorithm). In this study, regular assessments to monitor infusion reactions and infusion site reactions will be done. To ensure that reactions can be dealt with promptly, there will be at least 15 minutes between the end of infusion/injection in one subject and the start of infusion/injection in the next subject. No

more than 6 subjects will be dosed per day. Any reactions will be treated and taken into account in the dose continuation/escalation and toxicity rules (see Table 3). If anaphylactic reactions occur, the current "UK Treatment Guideline for Anaphylactic Reactions" of the UK Resuscitation Council will be followed (see Appendix 2: United Kingdom Resuscitation Council Anaphylaxis Algorithm).

Subjects who experience a severe reaction during administration of study drug that results in discontinuation of study drug should undergo all scheduled safety, immunogenicity, PK, and PD evaluations required by the protocol. Subjects will therefore be instructed to attend all scheduled visits and undergo all procedures per protocol.

Similar reactions could potentially occur with SC injections of mAbs.

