18.2. Analysis Populations

The safety population will consist of all subjects who receive at least 1 dose of study drug. Subjects in this population will be used for the safety analysis.

The PK population will consist of all subjects who have sufficient serum concentration data to enable the calculation of PK parameters. The PK population will be used for PK summaries.

The PD population will consist of all subjects who have sufficient total and free C5 concentration data and cRBC hemolysis data. The PD population will be used for PD summaries.

The immunogenicity analysis population will consist of all subjects who have a pre-dose and post-dose ADA sample collected.

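### Read literally, the SAP safety population leaves out a subject who receives only part of the dose; the protocol wording is unclear on the same case, and both need one clarifying sentence

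*SAP*

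**What the plan says.** The SAP (4.1, Analysis Populations) defines the set as follows: "The safety population will consist of all subjects who receive the protocol-defined, single dose of study drug". Protocol 18.2 has: "The safety population will consist of all subjects who receive at least 1 dose of study drug". The protocol synopsis agrees with 18.2: "All subjects who received at least 1 dose of study drug will be included in the safety analysis".

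SAP 4.4 runs every safety analysis on this population. SAP 4.1 also takes the immunogenicity, PD and PK populations from within it. The protocol does not nest them: sections 13.2, 14.2 and 18.2 define those sets by the samples or data available.

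The protocol foresees incomplete dosing. Section 12.6 says that an infusion may have to be stopped and that similar reactions could follow SC injection. It then says: "Subjects who experience a severe reaction during administration of study drug that results in discontinuation of study drug should undergo all scheduled safety", and goes on to name the immunogenicity, PK and PD evaluations. Section 10.3 adds: "Subjects who discontinue dosing will be instructed to return for follow-up visits as described in the Schedule of Assessments". The SC dose is physically divisible, under 12.5.1: "All doses of ALXN1210 SC or placebo SC will be administered by four 100-mg SC injections of 1 mL each". Neither document says how a partly dosed subject enters the analysis sets.

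**The concern.** The SAP phrase adds a condition that the protocol sentence lacks. A subject stopped after one to three injections, or part-way through the infusion, has not received the single 400 mg dose that the protocol defines. On a literal reading that subject leaves the safety tables and, through the nesting, the ADA table.

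Safety and tolerability of SC compared with IV is a primary objective, and ADA incidence is a named safety endpoint. Both documents plan only descriptive safety analyses, so the incidence tables carry the comparison. A stop caused by a reaction is informative about the drug. Removing that subject lowers the tabulated frequency of the kind of event the table is meant to show. The follow-up that protocol 12.6 requires would have been collected and then left out of the summaries.

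**Working it through.** **Texts compared for a subject who receives part of the dose**

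| Source | Condition | Partly dosed subject |
|---|---|---|
| SAP 4.1 | the one dose the protocol defines | out, if read literally; in, if the phrase only describes the single-dose design |
| Protocol 18.2, synopsis | at least one dose | in, if dose means any exposure; out, if dose means the full 400 mg, as in Table 7 |
| Protocol 14.2, 18.2 (immunogenicity) | pre-dose and post-dose ADA sample | in |
| SAP 4.1 (immunogenicity) | the same samples, within the safety population | follows the first row |

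**Outputs affected on the literal SAP reading.** These are the summary tables of treatment-emergent adverse events, laboratory values, vital signs and ECGs (SAP 4.4) and the ADA table (SAP 4.8).

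**Outputs not affected.** By-subject listings cover all enrolled subjects (SAP 5). Site evaluations, site pain and physical examination are listed only (SAP 4.4). Disposition covers all subjects, and the count of subjects per population would itself show an exclusion (SAP 4.3).

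**Group sizes** (protocol 8.2, SAP 3.2): active SC 4 + 20 = 24; IV 12; placebo SC 2 + 4 = 6; total 24 + 12 + 6 = 42.

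**Illustration.** Suppose one subject in an arm of n is incompletely dosed because of a reaction. With k subjects in the arm having that event, including this one, the table shows k/n if the subject is kept and (k − 1)/(n − 1) if excluded. Limits are exact (Clopper-Pearson) 95%; for zero events the upper limit is 1 − 0.025^(1/n).

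| Arm | Kept | Excluded |
|---|---|---|
| IV, only event | 1/12 = 8.3% (0.2% to 38.5%) | 0/11, upper limit 1 − 0.025^(1/11) = 28.5% |
| Active SC, only event | 1/24 = 4.2% (0.1% to 21.1%) | 0/23, upper limit 1 − 0.025^(1/23) = 14.8% |
| IV, one of two events | 2/12 = 16.7% | 1/11 = 9.1% |
| Active SC, one of two events | 2/24 = 8.3% | 1/23 = 4.3% |
| Overall column, only event | 1/42 = 2.4% | 0/41 |

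The shift can also go the other way. If an IV subject is stopped for a technical reason without an event, and another IV subject has one, 1/12 = 8.3% becomes 1/11 = 9.1%.

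The documents give no stop rate for SC dosing, so no probability is attached to these cases.

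**The case against.** The strongest reply is that the two documents may not disagree. Throughout the protocol a dose is the full 400 mg, and Table 7 counts four syringes as one dose. Read as strictly as the SAP, the protocol also excludes a subject stopped after two injections. The SAP phrase is followed by a list of the three treatments, which suggests that it merely describes a one-dose study. This largely stands. A reader might infer that the SAP deliberately narrowed the safety population, but nothing in it states that intent. What remains is an ambiguity in both texts, with an added qualifier in the SAP that makes the excluding reading easier.

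A second reply is that an exclusion would be visible and could be reversed. The Blind Data Review Meeting decides membership of each set. Protocol 8.1 says in general terms that enrolled subjects enter the analyses where appropriate. The listings are complete, adverse events during administration have their own listing, and the toxicity rules in protocol Table 3 apply to drug-related events whatever the analysis set. So the documents do not support a reading that a reaction would be hidden. Still, the meeting has no written criterion for partial doses, and a listing does not correct an incidence table.

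Third, early stops may be rare. For the completed single-dose IV study, protocol 5.1.1 reports that "no serious adverse drug reactions, treatment discontinuations, or deaths were reported". With N = 10 as given, 0/10 has an exact 95% upper limit of 1 − 0.025^(1/10) = 30.8%, so it neither establishes nor excludes a low rate, and it says nothing about SC.

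Two wider readings also fail. One is that any mis-dosed subject is lost. A full dose of the wrong treatment is arguably still a dose the protocol defines, and SAP 4.4 already groups adverse events by treatment actually received. The other is that loss from the PD summaries is a harm. Protocol 5.1.1 says of the PD effect: "The duration of the effect was longer following a 400-mg dose than a 200-mg dose". Leaving a partly dosed subject out of a 400 mg PD summary is therefore defensible.

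**Conclusion.** The point holds as a minor one. The SAP sentence, read as written, takes an incompletely dosed subject out of the safety and ADA tables, while the protocol sentence is open on the same case. The size is one subject per occurrence. In the worked examples the only event of its kind disappears from a group of 12 (8.3%) or 24 (4.2%).

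This rests on three conditions: at least one subject receives an incomplete or wrong amount, the SAP text is applied literally, and the Blind Data Review Meeting does not include the subject. If any of them fails, the effect is nil. For the tables to understate a reaction, the stop must also have been caused by that reaction. The documents do not support a stronger conclusion, whether of deliberate exclusion, of hidden events, or of damage to the PD or PK results.

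**What to change.** In SAP 4.1, define the safety population as all subjects who receive any amount of study drug, analysed by treatment actually received. State that this clarifies the wording of protocol 18.2. Draw the immunogenicity population from that set.

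Before the Blind Data Review Meeting, also state whether partly dosed subjects are flagged within the PD summaries or left out of them. Either choice is acceptable if it is written down in advance.

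The cost is one sentence for the safety population and one rule or footnote for the PD tables, in a SAP amendment before database lock. No new data, visits or analyses are needed.
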